11.4.2 Primary Analysis

The primary outcome, i.e. the four overall scores of the ISI of all follow-up time-points will be analyzed with a mixed effects linear model. The model will take into account the hierarchical structure of the data: multiple ISI scores per patient and clusters (cross-over). Because of the complexity of the data and the small number of clusters we assume that we will not be able to introduce random effects for patients and clusters. However, our first approach will still be a linear mixed model with the following co-variables: fixed intervention effect (TAU plus SleepExpert versus TAU plus sleep monitoring), fixed baseline ISI score effect, random patient effect (multiple ISI scores during follow-up), random cluster effect. Depending on model fit, we may need to simplify the model and modify the random effects. This model is pre-specified and the rationale for switching will be made explicit. The analysis will be made after all data has been collected by one of the principal investigators.

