4.2 Primary Objective

The primary objective is to assess whether there is a significantly greater reduction in self-assessed insomnia severity (as measured by the Insomnia Severity Index, ISI) across six months (interaction effect Group and Timepoint) in patients in the Tau plus SleepExpert group, compared to patients in the TAU plus sleep monitoring group.

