6. STUDY DESIGN

6.1 General study design and justification of design

This project is a prospective randomized controlled clinical pilot trial with a cluster-crossover design

involving two groups: An interventional group (TAU, plus SleepExpert) and a control group (TAU plus sleep monitoring).

Two different wards in the trial site (UPD Bern) will constitute the clusters. The study is conceptualized with a crossover, i.e. clusters (wards) will first be randomized to one of the groups for a duration of 4 months. After a washout-phase of two months, they will then be allocated to the other group for another 4 months. The order (TAU plus SleepExpert first vs. TAU plus sleep monitoring first) will be randomly allocated in a 1:1 fashion.

A total of 60 patients will be included. Patients will be assessed before the intervention (T0) and at the following time-points after the start of the intervention: 1 week (T1), 2 weeks (T2), 12 weeks (T3) and 26 weeks (T4).

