7.3 Assignment to study groups

The two clusters (UPD wards) will be assigned to one of the following two study sequences – while one cluster will follow the first sequence, the other one will follow the second sequence. Which ward will follow which study sequence will be randomly assigned.

- TAU plus SleepExpert first for 4 months; fade-out for one month; wash-out for one month; TAU plus sleep monitoring for 4 months
- TAU plus sleep monitoring for 4 months; fade-out for one month, wash-out for one month; TAU plus SleepExpert for 4 months

During the TAU plus SleepExpert and TAU plus sleep monitoring phases, patients will be actively recruited. During the fade-out phases, no active recruitment will take place, but already recruited patients will be able to complete their treatment. During the wash-out phase, no recruitment and no study-related treatment will take place.

Depending at which stage of the study the ward stands at the time point when a subject is admitted to the ward, her or she will either receive TAU plus SleepExpert or TAU plus sleep monitoring, or, if admitted during the wash-out phase, the subject will not be able to participate in the trial.

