11.2 Determination of Sample Size

A power analysis was conducted with G-Power (Faul, Erdfelder, Lang, & Buchner, 2007). Assuming an alpha error level of 0.05 (two-sided) and a power of 0.8, a total sample size of n=60 will be sufficient to detect a medium effect (Cohen's d=0.65). This is a pilot trial with the primary aim of collecting qualitative experience and preliminary efficacy data. A large confirmatory trial will be conducted if the results of this pilot trial are encouraging.

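### With two wards crossed once, the SleepExpert effect coincides with the ward-by-phase interaction; the planned model and power calculation leave ward-phase variation out, so the p-value and interval are too optimistic if that variation is above zero.

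*Combined protocol and SAP*

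**What the plan says.** Section 6.1 sets the design: "Two different wards in the trial site (UPD Bern) will constitute the clusters". Each ward has two 4-month phases: "After a washout-phase of two months, they will then be allocated to the other group for another 4 months". Section 7.3 puts one ward in each order: "while one cluster will follow the first sequence, the other one will follow the second sequence". Section 6.1 also fixes the total: "A total of 60 patients will be included".

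Section 11.4.2 describes a linear mixed model for the four follow-up ISI scores and says: "The model will take into account the hierarchical structure of the data: multiple ISI scores per patient and clusters (cross-over"). The terms listed are fixed intervention, fixed baseline ISI, random patient and random cluster. No phase term and no ward-by-phase term is listed. The section expects that the random effects may not be fittable with so few clusters and allows simplification, but names no replacement model. Section 11.4.1 adds only that the crossover design will be considered.

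Section 11.2 reports a G*Power calculation with two-sided alpha 0.05, power 0.8 and Cohen's d = 0.65, and concludes that "a total sample size of n=60 will be sufficient to detect a medium effect". It mentions no ICC or design effect. Section 4.2 words the objective in terms of significance: "The primary objective is to assess whether there is a significantly greater reduction in self-assessed insomnia severity".

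**The concern.** Section 11.4.2 offers the model as one that handles the clustered crossover. A ward effect handles only stable differences between the wards, and the crossover already removes those. What can move the SleepExpert estimate is a shift in one ward during one phase. In this layout such a shift cannot be told apart from a treatment effect.

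The documents make some shared variation plausible. Usual care is individualised and unrestricted (8.1.1, 8.7). SleepExpert starts in a group session and is coached by ward nurses (8.1.1), so patients in the same ward-phase share deliverers.

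At stake is how the result is read. Sections 4.2, 4.3 and 11.1 are worded around significance, and 11.2 makes a large confirmatory trial depend on encouraging pilot results. An interval that is too narrow could carry more weight in that decision than the design supports.

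**Working it through.** **Inputs.** From 6.1, 7.3 and 11.2: 2 wards, 2 phases, one ward per sequence, N = 60, d = 0.65, two-sided alpha 0.05, target power 0.80. Assumed, because the documents do not give them: equal cells of m = 60/4 = 15 patients, and a ward-phase ICC of 0.01, 0.02 or 0.05. Here ICC is the ward-phase share of patient-level variance once the ward effect has been removed. The calculation uses one outcome per patient without baseline adjustment, so it approximates the planned repeated-measures model.

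**1. The plan's own figure.** A two-sample two-sided t-test with d = 0.65 and 80% power needs 39 per arm, or 78 in total. With N = 60 the power is 69.7% (71.1% by the normal approximation). N = 60 is reproduced by a one-sided t-test (30 per arm, 80.0%). It is also reproduced two-sided under unstated assumptions: a baseline correlation near 0.47, or four follow-up scores correlated at about 0.7. None of these includes clustering.

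**2. What the contrast is.** Let ward A receive SleepExpert in phase 1 and ward B in phase 2. The effect estimate is (A1 − A2 + B2 − B1)/2. A constant added to both A cells cancels, and so does a constant added to both phase-1 cells. A shift in one cell alone does not cancel. This is the ward-by-phase interaction.

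**3. Degrees of freedom for ward-phase variance.** There are four cell means. Intercept, ward, phase and arm use four parameters and leave 0 df. The listed terms omit phase, so intercept, ward and arm leave 1 df. With 1 df the two-sided t critical value is 12.7, and cell-level power for d = 0.65 is only about 12% to 16%.

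**4. Variance of the contrast.** With total variance 1:

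- True variance = (1/4) × 4 × [ICC + (1 − ICC)/m] = ICC + (1 − ICC)/m.
- Variance reported by a model without a ward-phase term ≈ (1 − ICC)/m.
- SE multiplier = sqrt([1 + (m − 1)ICC]/(1 − ICC)).
- Design effect relative to 60 independent patients: DE = 1 + (m − 1)ICC. Effective N = 60/DE.
- Actual type I error = 2 × [1 − Φ(1.96/multiplier)].
- Power (normal approximation, variance treated as known) ≈ Φ(0.65 × sqrt(effective N/4) − 1.96).

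| ICC | True variance | Reported variance | SE multiplier | Type I error | DE | Effective N | Power |
|---|---|---|---|---|---|---|---|
| 0 | 0.0667 | 0.0667 | 1.00 | 5.0% | 1.00 | 60 | 71% |
| 0.01 | 0.0760 | 0.0660 | 1.07 | 6.8% | 1.14 | 53 | 65% |
| 0.02 | 0.0853 | 0.0653 | 1.14 | 8.6% | 1.28 | 47 | 60% |
| 0.05 | 0.1133 | 0.0633 | 1.34 | 14.3% | 1.70 | 35 | 49% |

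**5. Simulation check.** I ran 40,000 null trials per setting, with 15 patients per cell and patient-level regression. At ICC 0, 0.01, 0.02 and 0.05, rejection was 5.0%, 6.7%, 8.5% and 13.9% with ward, phase and arm fitted. With phase omitted it was 5.1%, 6.7%, 8.3% and 13.9%. Adding a phase term therefore does not cure the problem.

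**The case against.** Much of the case for the plan is fair. Section 11.4.2 acknowledges the small number of clusters and promises an explicit rationale for any switch of model. Section 11.2 calls the trial a pilot for qualitative experience and preliminary efficacy data. Section 11.4 defers detail to an SAP that is not in the documents. Baseline ISI is in the model and screening is standardised across wards (7.2), which limits case-mix shifts. Stays typically last one to eight weeks (8.1.1), so the week-12 and week-26 scores, two of the four, usually fall after discharge, when conditions on the ward act less directly.

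These points bear on how large the variation may be and how serious the point is. None of them adds the missing condition. The acknowledgement in 11.4.2 concerns patient and ward effects, and no later SAP can estimate a variance for which the design leaves 0 or 1 df.

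Three stronger readings are tempting, and the documents do not support them:

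- **The test is certainly invalid.** With no ward-phase variation, the approximating ward-adjusted analysis runs at 5%. The documents give no ICC, so the inflation is conditional and its size unknown.
- **The variance has exactly 0 df under the plan.** That count includes a phase term the plan does not list. The listed terms leave 1 df, although it has little practical use.
- **The sample size is simply wrong.** N = 60 does not follow from a plain two-sided t-test, but it could follow from adjustment or repeated measures that 11.2 does not mention.

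**Conclusion.** The point holds as a conditional one. The treatment contrast coincides with the ward-by-phase interaction, the one cluster term in 11.4.2 cancels from that contrast, and 11.2 states no allowance for clustering. If ward-phase variance is above zero, the reported p-value and interval are too optimistic, and the trial's own data cannot show whether it is. At assumed ICCs of 0.01 to 0.05 with 15 patients per cell, type I error is about 7% to 14% and effective N about 53 to 35. These figures rest on assumed ICCs, equal cells and a single unadjusted outcome, so they show a plausible range rather than predict this trial. The point ranks below a must-fix, because the trial is a pilot and the size of the effect is unknown. It still affects what the trial may conclude.

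**What to change.** 1. **Section 11.4.2.** State that the model-based interval is conditional on no ward-by-phase variation. Report the primary estimate with intervals for assumed ward-phase ICC 0, 0.01, 0.02 and 0.05, multiplying the reported SE by sqrt([1 + (m − 1)ICC]/(1 − ICC)). At m = 15 the factors are 1.00, 1.07, 1.14 and 1.34; recompute them for the actual cell sizes. Define the ICC on the baseline-adjusted patient-level mean follow-up ISI. The square root of the design effect (1.07, 1.13, 1.30) should not be used here, because it is relative to total variance, whereas the reported SE reflects variance within cells. Also report the four ward-phase mean changes.
2. **Sections 4.2, 4.3 and 11.1.** Keep the objectives, and add that any significance statement carries this condition and is preliminary. Rewording them as estimation is optional.
3. **Section 11.2.** State that the calculation assumes no ward-phase clustering, and restate the power. A two-sided t-test with N = 60 and d = 0.65 gives about 70% at ICC 0. The normal approximation gives about 65%, 60% and 49% at ICC 0.01, 0.02 and 0.05. If N = 60 rests on adjustment or repeated measures, state those assumptions.

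The cost is wording, one extra table and a less favourable stated power. No ward, patient or assessment is added.

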Study Schedule:	
Month Year of First-Participant-In (planned): August 2021 Month Year of Last-Participant-Out (planned): January 2024

Investigator(s):	
[name]. [name] (Sponsor-Investogator) Institution: UPD Bern Position: Chefarzt, Stv. Ärztlicher Direktor Address: [name] Mail: [contact]
 
Dr. phil. [name] (Sub-Investigator) Institution: UPD Bern Position: Psychologist Address: [name] Mail: [contact]

Study Centre(s):	
Single-centre Universitäre Psychiatrische Dienste Bern

Statistical Considerations:	
Our primary analysis will be a linear mixed model with the following co-variables: fixed intervention effect (TAU plus SleepExpert versus TAU plus sleep monitoring), fixed baseline ISI score effect, random patient effect (multiple ISI scores during follow-up), random cluster effect. Depending on model fit, we may need to simplify the model.

GCP Statement:	
This study will be conducted in compliance with the protocol, the current version of the Declaration of Helsinki, the ISO EN 14155 norm as well as all national legal and regulatory requirements.

ABBREVIATIONS

AE	Adverse Event
ASR	Annual Safety Report
BASEC	Business Administration System for Ethical Committees, (https://submissions.swissethics.ch/en/)
CA	Competent Authority (e.g. Swissmedic)
CEC	Competent Ethics Committee
CRF	Case Report Form
ClinO	Ordinance on Clinical Trials in Human Research (in German: KlinV, in French: OClin, in Italian: OSRUm)
eCRF	Electronic Case Report Form
CTCAE	Common terminology criteria for adverse events
DSUR	Development safety update report
GCP	Good Clinical Practice
IB	Investigator's Brochure
Ho	Null hypothesis
H1	Alternative hypothesis
HRA	Federal Act on Research involving Human Beings (in German: HFG, in French: LRH, in Italian: LRUm)
IMP	Investigational Medicinal Product
IIT	Investigator-initiated Trial
ICH	International Council for Harmonisation of Technical Requirements for Pharmaceuticals for Human use
ISO	International Organisation for Standardisation
ITT	Intention to treat
MD	Medical Device
MedDO	Medical Device Ordinance (in German: MepV, in French: ODim)
PI	Principal Investigator
SAE	Serious Adverse Event
SDV	Source Data Verification
SOP	Standard Operating Procedure
SPC	Summary of product characteristics
SUSAR	Suspected Unexpected Serious Adverse Reaction
TMF	Trial Master File

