6.2.3 Other methods of minimising bias

- The primary applicant is a staff member at the sleep clinic of the University Psychiatric Services Bern. The resources at this established, specialized sleep clinic will ensure that included patients are carefully diagnosed, i.e. that only patients fulfilling the defined eligibility criteria will be included. This ensures generalizability of the results to the intended population.
- Study attrition and reasons for dropout will be carefully documented throughout the study period.
- An intention to treat analysis will be provided since a per-protocol analysis may result in biased effects if many patients drop out due to (perceived) inefficacy.
- The outcome measures are widely used, valid, and reliable measures that have been recommended by experts for the research assessment of insomnia (Buysse, Ancoli-Israel, Edinger, Lichstein, & Morin, 2006).
- Therapists will be experienced, well-trained, and supervised.
- The trial will be registered in a publicly accessible database before recruitment of the first subject. Hypotheses and the analysis plan will be made publicly available. This precludes that the analysis plan is changed after inspection of the data ("fishing for significances").

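### The primary model may be simplified on fit without any rule that within-patient correlation stays; if it were ignored, the error rate for the averaged intervention term would be about 13-20%, not 5%

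*Combined protocol and SAP*

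**What the plan says.** Section 11.4.2 states that "the four overall scores of the ISI of all follow-up time-points will be analyzed with a mixed effects linear model" and that the model will respect the hierarchy of repeated scores within patients and of patients within clusters. Citing the complexity of the data and the small number of clusters, it then says "we assume that we will not be able to introduce random effects for patients and clusters". The first attempt nevertheless has fixed effects for intervention and baseline ISI and, as random terms, "random patient effect (multiple ISI scores during follow-up), random cluster effect". Next comes the release clause: "Depending on model fit, we may need to simplify the model and modify the random effects". The rationale for any switch is to be made explicit. The synopsis (Statistical Considerations) carries a shorter form of the same clause: "Depending on model fit, we may need to simplify the model".

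No fallback model is named, nor any order of removal or alternative way of handling the correlation. Section 11.4.3 applies the same procedure to the BSI and BDI. Section 6.2.3 says of prior registration and publication of the plan: "This precludes that the analysis plan is changed after inspection of the data".

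**The concern.** Section 11.4.2 treats two different difficulties as one. The trial has 2 wards (Section 6.1), and a variance component with two levels cannot be usefully estimated. The patient component has 60 levels with four scores each and presents no such problem. Because both are placed together among the effects expected to fail, the patient effect becomes a candidate for removal for a reason that applies only to wards.

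The patient effect, or an equivalent residual covariance, tells the model that four scores from one person are not four independent pieces of evidence. If it goes and nothing replaces it, up to 60 x 4 = 240 scores count as independent. The standard error of the averaged intervention effect is then too small and its confidence interval too narrow. Section 11.2 makes a large confirmatory trial depend on encouraging results here, so a false positive would have consequences even in a pilot.

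**Working it through.** **The plan's own figure.** The documents state no error rate for a fallback model. The only related figure is the sample size in Section 11.2: 60 patients for d = 0.65, "Assuming an alpha error level of 0.05 (two-sided) and a power of 0.8". A plain two-group comparison does not reproduce it. The normal formula gives 2 x (1.960 + 0.842)^2 / 0.65^2 = 37.2, so 38 per arm or 76 in total; the t-test gives 39 per arm or 78. With 60 patients, power is about 70-71%. That is a separate matter; only the number of patients is used below.

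**Inputs from the documents.** 60 patients; m = 4 follow-up ISI scores at weeks 1, 2, 12 and 26; two-sided alpha 0.05; baseline ISI as covariate; 2 wards.

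**Assumptions.** 30 patients per condition, no missing scores, no ward or ward-period variance, and a residual correlation r between any two follow-up scores of the same patient after baseline adjustment. The documents give no r, so a range is shown.

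**Step 1: plausible r.** If any two ISI scores, including T0, correlate at rho, then after adjustment for T0

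r = (rho - rho^2) / (1 - rho^2) = rho / (1 + rho).

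For rho = 0.3, 0.5 and 0.7 this gives r = 0.231, 0.333 and 0.412. Under this structure r stays below 0.5. Values up to 0.7 require follow-up scores to correlate more strongly with each other than with T0.

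**Step 2: averaged intervention term, four scores treated as independent.** The true variance is (1 + 3r) times the variance the model reports, so

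type I error = 2 x [1 - Phi(1.96 / sqrt(1 + 3r))].

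| r | 1 + 3r | Error, formula | Error, simulation |
|---|---|---|---|
| 0.20 | 1.60 | 12.1% | 12.5% |
| 0.23 | 1.69 | 13.2% | - |
| 0.30 | 1.90 | 15.5% | 15.2% |
| 0.40 | 2.20 | 18.6% | 19.0% |
| 0.45 | 2.35 | 20.1% | 20.2% |
| 0.50 | 2.50 | 21.5% | 22.2% |
| 0.70 | 3.10 | 26.6% | 27.6% |

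The simulation used 4,000 runs per row and ordinary regression on 240 rows with treatment and baseline. The standard error is understated by 1 - 1/sqrt(1 + 3r), which is 23% at r = 0.23 and 33% at r = 0.41.

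**Step 3: sensitivity.** Correlation that decays over weeks 1, 2, 12 and 26 (mean pairwise 0.23-0.43) gives 13.0-19.5% by simulation. With three scores per patient (variance factor 1 + 2r), r = 0.23-0.45 gives about 10-16%.

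**Step 4: BSI and BDI.** Table 1 and Section 9.3.2 give two post-baseline visits (T2, T4), so the factor is 1 + r. For r = 0.23 and 0.41 the error is 7.7% and 9.9%. Section 5.2 lists four post-baseline visits for the BSI; if that schedule applied, Step 2 would hold for it.

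**Step 5: group-by-time contrast.** For a within-patient contrast under equal correlation the factor is 1 - r. At r = 0.23, 2 x [1 - Phi(1.96 / sqrt(0.77))] = 2.5%; at r = 0.41, with factor 0.59, it is 1.1%. Ignoring the correlation makes this test conservative.

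**Step 6: correlation retained.** When each patient contributes one mean follow-up score, adjusted for baseline, the simulated error is 4.5-5.5% for every r from 0 to 0.7.

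**The case against.** A reader might infer that the plan's fallback is to drop the patient effect. The documents do not support that. No fallback is named, and the sentence can mean that the two random effects cannot be fitted together. Removing only the ward effect would satisfy the release clause. The same section commits to a mixed model that reflects repeated scores within a patient, and ordinary regression on 240 rows would break that commitment. Nor does losing a random intercept force independence, since a residual covariance structure, GEE or robust standard errors could take its place. All of this stands, and it limits the point to what the text permits.

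A second objection is that the primary objective in Section 4.2 is a group-by-time interaction, for which the mistake would be conservative. That also stands for such a contrast. But the model listed in 11.4.2 has no time or interaction term; its only treatment term is the averaged effect, to which the inflation applies.

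There are also safeguards. An SAP is due at the start of recruitment (11.4), it is version-controlled with post-hoc changes reported (11.4.5), and analysts are to be blinded (6.2.2). These narrow the scope for choosing a model by its result. They do not say which term must stay, and reporting a switch does not repair a standard error that is too small. Finally, this is a pilot seeking preliminary efficacy data, which lowers the stakes without removing them.

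**Conclusion.** The point holds in a limited form. Section 11.4.2 rests on a mistaken premise, that a shortage of clusters bears on the patient effect, and so leaves open a primary analysis with an invalid standard error. It anticipates and permits that analysis; it does not prescribe it.

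The size is conditional on three things: the patient effect is dropped, nothing else handles the correlation, and the averaged intervention term is tested. It should not be read as the trial's expected error rate, nor carried over unchanged to the BSI and BDI or to the interaction in Section 4.2, where the size or the direction differs. The range depends on a residual correlation that the documents do not give, and the calculation leaves out ward and ward-period variance.

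**What to change.** In 11.4.2, and so for 11.4.3, replace the open clause with a fixed order:

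1. A repeated-measures model with unstructured covariance over the four follow-up visits (4 x 5 / 2 = 10 parameters).
2. If that does not converge, a random patient intercept.

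State that within-patient correlation is retained in every version. Replace the random cluster effect by fixed effects for ward and period. Include visit, and treatment-by-visit if the interaction in Section 4.2 is the target. Choose the step on convergence alone, before the treatment coefficient is seen. Make the synopsis agree.

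The cost is a few lines of text and one or two degrees of freedom, with no new patients or data. One limitation remains and should be stated. Two wards in two periods give four cells and three degrees of freedom between them, all used by ward, period and treatment. Ward-by-period correlation therefore still cannot be fully accounted for.

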Clinical Phase:	Medical Device Study Risk category A, Phase of development I
Background and Rationale:	
Mental disorders are highly prevalent, undertreated, and associated with substantial disability and reduced quality of life (Demyttenaere et al., 2004). One third of patients with mental disorders comorbidly suffer from insomnia disorder according to the Diagnostic and Statistical Manual of Mental Disorders (American Psychiatric Association, 2013, S. 5). Following current European and American practice guidelines for adult patients, cognitive behavioral therapy for insomnia (CBT-I) is the first line treatment (Qaseem et al., 2016; Riemann et al., 2017). Various adaptations of CBT-I for different target groups and settings have been developed. One of them is Brief Behavioral Treatment for Insomnia (BBT-I), consisting of four sessions centering of bedtime restriction (Troxel et al., 2012). This demonstrates that brief versions of CBT-I can be similarly effective as the complete program. The intervention "SleepExpert" is based on BBT-I as a brief version of CBT-I, the first-line treatment for insomnia according to current guidelines. There has been a feasibility study, however this study was uncontrolled. In the proposed project, we aim to compare treatment as usual (TAU) plus SleepExpert to TAU plus sleep monitoring in a pilot randomized controlled trial. The objective is to target sleep to improve mental health and to investigate the efficacy of SleepExpert for the improvement of sleep and mental health.

Objective(s):	
The primary objective is to assess whether there is a significantly greater reduction in self-assessed insomnia severity (as measured by the Insomnia Severity Index, ISI) across six months (interaction effect Group and Timepoint) in patients in the Tau plus SleepExpert group, compared to patients in the TAU plus sleep monitoring group.
 
The secondary objective is to assess whether there is a significantly greater improvement in general mental health (Brief Symptom Inventory) across six months (interaction effect Group and Timepoint) in patients in the TAU plus SleepExpert group, compared to patients in the TAU plus sleep monitoring group.

Outcome(s):	The primary outcome will be insomnia severity measured with the Insomnia Severity Index (ISI) (Bastien et al., 2001). The ISI will be administered before the intervention (T0) and one, two, 12, and 26 weeks after the start of the intervention

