4.3 Secondary Objectives

The secondary objective is to assess whether there is a significantly greater improvement in general mental health (Brief Symptom Inventory) across six months (interaction effect Group and Timepoint) in patients in the TAU plus SleepExpert group, compared to patients in the TAU plus sleep monitoring group.

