11. STATISTICAL METHODS

11.1 Hypothesis

Hypothesis: SleepExpert improves insomnia and general mental health in patients with severe mental disorders.

Primary objective: To assess whether there is a significantly greater reduction in self-assessed insomnia severity (as measured by the Insomnia Severity Index, ISI) across six months (interaction Group x Time) in patients in the Tau plus SleepExpert group, compared to patients in the TAU plus sleep monitoring group.

Secondary objective: To assess whether there is a significantly greater improvement in general mental health (Brief Symptom Inventory) across six months (interaction Group x Time) in patients in the TAU plus SleepExpert group, compared to patients in the TAU plus sleep monitoring group.

Exploratory objectives: Additional objectives include the effect of TAU plus SleepExpert versus TAU plus SleepMonitoring on the following parameters:

- severity of depressive symptoms (Beck Depression Inventory, BDI)
- mood, tiredness, concentration, and subjective sleep quality (self-constructed visual analogue scales)
- daytime sleepiness (Epworth Sleepiness Scale)
- medication
- hospitalization

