11.4.3 Secondary Analyses

Continuous outcomes (Brief Symptom Inventory, Beck Depression Inventory) will also be analyzed by a mixed effects linear model using the same procedure used to estimate the primary outcome. Binary outcome data will be analysed using mixed effect logistic regression with odds-ratio as the effect measure. The number of hospitalizations will be also analyzed by a mixed effects model. Interim analyses

No planned interim analysis

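### The objectives name a Group x Time interaction across six months, but the pre-specified model estimates one baseline-adjusted average effect, with no visit term and no estimate by visit (SHOULD-FIX)

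*Combined protocol and SAP*

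**What the plan says.** **Objectives.** The synopsis and 4.2 ask for a greater ISI reduction "across six months (interaction effect Group and Timepoint"). Section 4.3 asks for the same on the secondary outcome: "improvement in general mental health (Brief Symptom Inventory) across six months (interaction effect Group and Timepoint"). Section 11.1 repeats both as "across six months (interaction Group x Time").

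**Model.** Section 11.4.2 takes the four follow-up ISI scores (weeks 1, 2, 12 and 26) as responses. The listed terms are "fixed intervention effect (TAU plus SleepExpert versus TAU plus sleep monitoring), fixed baseline ISI score effect, random patient effect", plus a random cluster effect. The synopsis gives the same list and ends "random cluster effect. Depending on model fit, we may need to simplify the model". Section 11.4.2 calls this model pre-specified, promises a rationale for any switch, and adds "Depending on model fit, we may need to simplify the model and modify the random effects". It also warns that "we assume that we will not be able to introduce random effects for patients and clusters". Nothing says that a time term would be added.

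**Secondary outcome.** Under 11.4.3 the BSI and BDI "will also be analyzed by a mixed effects linear model using the same procedure used to estimate the primary outcome".

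**Related provisions.** A SAP is to be written when recruitment starts (11.4); it is not among the documents reviewed. Section 11.5 plans multiple imputation above a missing-data threshold of 5-10%. Section 11.2 makes a large confirmatory trial conditional on encouraging results here.

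**The concern.** The hypothesis and the test are different objects. A Group x Time interaction asks whether the groups' courses over time differ. The listed model has one group coefficient, taken to be the same at every visit. No parameter in it is an interaction, and none belongs to a particular visit.

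Two things are at stake. First, either the stated hypothesis or the stated model could later be called the planned test, which weakens the protection that 6.2.3 seeks by publishing both. Second, a single average could be reported as an effect across six months when it comes mainly from the first two weeks, or could hide a benefit that appears late. Inpatient stays are typically one to eight weeks (8.1.1), and the third phase of the intervention is self-management after discharge. Whether a difference persists to T4 is thus a natural question when deciding on a larger trial.

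**Working it through.** The plan gives no figure on this point, so there is none to reproduce. The check compares terms and then works out what the coefficient averages.

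**1. Terms side by side**

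| Element | Objectives (synopsis, 4.2, 4.3, 11.1) | Model (synopsis, 11.4.2, 11.4.3) |
|---|---|---|
| Group | yes | yes |
| Visit or time | yes | not listed |
| Group x visit | yes, named as the effect | not listed |
| Baseline score | part of the change over time | covariate |

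**2. What the coefficient estimates.** Write the model as Y(i,t) = a + b·Group(i) + c·ISI0(i) + random patient + random cluster + error, for t = weeks 1, 2, 12, 26. Group and baseline do not change within a patient. Leaving the cluster term aside, with complete data the estimate of b is therefore the analysis of covariance on each patient's mean of four scores:

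b = (d1 + d2 + d12 + d26) / 4, where dt is the baseline-adjusted difference at week t.

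Each visit has weight 1/4. Weeks 1 and 2 together carry 2/4 = 50%, and week 26 carries 25%. In one simulated complete data set, the random-intercept estimate (-0.4403) equalled the mean of the four visit-specific estimates (-0.4403), with or without visit in the model.

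**3. Different courses, similar averages.** The profiles are assumptions; 0.65 SD is borrowed from 11.2 as a scale.

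| Assumed difference at weeks 1, 2, 12, 26 (SD) | Average | At week 26 |
|---|---|---|
| 0.65, 0.65, 0.65, 0.65 | 0.65 | 0.65 |
| 0.65, 0.65, 0.3, 0 | 1.60/4 = 0.40 | 0 |
| 0.65, 0.65, 0, 0 | 1.30/4 = 0.325 | 0 |
| 0, 0, 0, 0.65 | 0.65/4 = 0.16 | 0.65 |

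The distortion can go either way. The early-only benefit gives twice the average of the late-only one (0.325 against 0.16), although only the latter is present at six months.

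**4. The BSI.** Table 1 and 9.3.2 collect it at T0, T2 and T4, so each of its two follow-up visits would carry 50%. Section 5.2 lists all visits instead. The weights in step 2 therefore apply to the ISI only.

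**5. Dropout.** With complete data, omitting visit leaves b unchanged. With unequal dropout it does not, because the group that loses more patients contributes fewer late scores. A simulation assumed no treatment effect, improvement in both groups rising from 0.2 SD at week 1 to 1.0 SD at week 26, correlation 0.5, and loss before week 12 of 50% in one group against 10% in the other. The listed model without its cluster term gave a spurious group effect of about 0.10 SD, against the group with more loss. Adding visit brought it close to zero.

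**6. The obvious repair can fail.** Group x visit on T1-T4 alone compares d1, d2, d12 and d26 with one another. For a constant benefit of 0.65 SD all these contrasts are 0.65 - 0.65 = 0, so the test has no power against exactly the result hoped for. Only when T0 is also a response does a constant follow-up benefit appear as an interaction (0 at T0, 0.65 afterwards).

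**The case against.** **The mismatch is largely one of terms.** The operative phrase in the objectives is a greater reduction. With T0 as covariate and T1-T4 as responses, the group coefficient is a legitimate one-degree-of-freedom test of that. This stands. A reader might infer that the primary hypothesis goes untested; the documents do not support that. What goes untested is the interaction that they name.

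**Week 26 was never promised.** This also stands. A reader might infer that the protocol breaks a commitment to a six-month test, but no section names T4 as the primary contrast. A T4 estimate is a useful addition, not a missing obligation.

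**Imputation deals with dropout.** In part. If 11.5 fills all visits using visit-specific information, every patient has four values and omitting visit no longer matters; below the threshold little is missing. But 11.5 gives no imputation model, so the risk is reduced, not removed.

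**The SAP will settle it, and this is a pilot.** Section 11.4 leaves models and outputs to the SAP, and version control and publication (11.4.5, 6.2.3) limit later choice. Section 11.2 gives the main aim as qualitative experience and early efficacy evidence, and does not tie an encouraging result to a p-value. This lowers the severity. It does not remove the contradiction, because 11.4.2 already describes its model as pre-specified.

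**Early visits may understate benefit.** Agreed: 10.3.1 foresees temporary worsening of sleep. That is a further reason to report by visit.

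**Conclusion.** The point holds as a SHOULD-FIX, and the plan is wrong as written: objective and model disagree for both the ISI and the BSI. The model tests a greater baseline-adjusted average reduction; it does not test an effect that varies over time and gives no visit-specific estimate.

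That conclusion rests on the text alone. The 50% and 25% weights need complete ISI data. The 0.40 and 0.16 SD averages rest on assumed profiles, and the 0.10 SD dropout effect on an assumed, large imbalance in loss with no imputation. None of these predicts this trial's result. A reader might take them as evidence that the primary result will be biased or driven by the first two weeks; they show only that the average alone could not reveal it.

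**What to change.** Before outcome data are seen:

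1. Restate the objectives in the synopsis, 4.2, 4.3 and 11.1 as the baseline-adjusted average group difference over follow-up, and keep that as the single primary test.
2. Add categorical visit to the model in the synopsis and 11.4.2.
3. Add group x visit to report the difference with its interval at each visit, including T4, as supporting. State that the primary estimate is the equal-weight average of these.
4. Apply the same choice to the BSI at the visits where it is collected, and reconcile 5.2 with Table 1 and 9.3.2.

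Handle the patient and ward terms as 11.4.2 already allows.

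If the interaction is truly intended, model T0-T4 as responses with group x visit and name one joint test or one contrast in advance. Do not use group x visit on T1-T4 alone. If T0 means are constrained to be equal, state this as an assumption, because only two wards are randomised and the information sheets differ by arm.

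**Cost.** The recommended route needs no new data: wording and a few degrees of freedom. The alternative loses power against a constant benefit. At 0.65 SD, the joint T0-T4 test has about 0.71, against about 0.98 for the average (illustration: 30 per group, correlation 0.5, no ward effect, no dropout).
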